### ***Word sentence association paradigm***

Word sentence association paradigm (WSAP) was used to assess the interpretation bias in youth with social anxiety (Beard & Amir, 2009). Following the appearance of a fixed cross (500ms), an ambiguous sentence describing the social situation would be presented in the center of the screen (2000ms). Then, a word would appear at random for 500ms: the word might imply a threatening interpretation (e.g., “boring” or “rejection”), or imply a benign one (e.g., “captivating” or “accepted”). Participants were asked to decide whether the word was related to the ambiguous sentence (“F” for

relevant and “J” for irrelevant). There were 30 ambiguous sentences in a block, corresponding to 30 threatening words and 30 benign words, for a total of 60 word-sentence pairs. The word-sentence pairs would be presented in random order, and no pairs were repeated. This study calculated the percentage of threaten and benign interpretations that participants endorsed as being related to the sentence, which was prescribed as the primary result of interpretation bias. We also recorded the response time and calculated the bias index (BI): threat BI = response times (reject threat – endorse threat) and benign BI = response times (endorse benign – reject benign).

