### **Interventions and study procedures**

The whole HD-tDCS intervention process was 10 sessions for 5 consecutive days (20 minutes each session and 2 sessions a day). All participants received active or sham HD-tDCS stimulation via a device from Soterix Medical, Inc (Woodbridge, NJ, USA). According to the 10/20 International EEG System, a “4 x 1 ring set-up” was placed in F3, FP1, FT7, C3 and FZ. F3 is the central anode electrode, which refers to the left

DLPFC, surrounded by the other 4 return cathode electrodes (Heeren et al., 2016; Jafari et al., 2021; Liu et al., 2023; Müller et al., 2022; Nejati et al., 2021; Parlikar et al., 2021). Both the tDCS group and the sham group were given electric current at the same electrode position. Normally, the current gradually rose to 2mA for the first 30 seconds, then continued for 20 minutes and then dropping to 0mA at the end of the stimulation. In the sham group, the current ramped up to 2mA for 30 seconds at the start and end of the stimulus and then ramped down without the participants' being aware of it, generating the same sensation as the active condition. During the intervention, participants were asked to maintain a relaxed and immobile posture.

Prior to the study, participants completed an enrollment screening questionnaire to determine their suitability for tDCS intervention. Participants who met the inclusion criteria were randomly divided into the tDCS and the sham group. Both two groups received 10 sessions of stimulation with 3 hours intervals between daily sessions (2 sessions daily, 5 days in total). Psychological symptoms (including social anxiety symptoms, cognitive bias and trait anxiety) and cognitive bias task performance (including dot probe task, word-sentence association paradigm, free recall and recognition task) were assessed before the first tDCS stimulation (pre-test) and after the last tDCS stimulation (post-test). According to the Latin square, the order of the three cognitive bias tasks was randomly counterbalanced among the participants. Finally, in order to ensure the safety of the tDCS stimulation and to compare the perception of this stimulation between different groups, a side-effect checklist was filled out by the participants after each session of stimulation. In addition, psychological symptoms were assessed again at 4 weeks follow-up. Participants in the entire experiment were rewarded with 280 RMB.

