### *Dot probe task*

Dot probe task is a common experimental paradigm for measuring attention bias (MacLeod et al., 1986). After appearance of a fixed cross in the center of the computer screen, a pair of faces appear side by side. Then, a probe appears on the location previously occupied by one of the two faces. Participants were asked to response the location of the probe as quickly as possible and press the appropriate keys to answer. If the probe was presented at a location that matched the attention, participants would

response more quickly than the mismatched location. In current study, the experimental task included 40 facial stimuli (20 male and 20 female), forming 30 face pairs (20 neutral-angry and 10 neutral-neutral combinations). Based on valence scores from preliminary testing, angry faces were categorized as either high-intensity and low-intensity. All these faces were selected from the Chinese facial affective picture system (Gong et al., 2011). The number of trials for each type of stimuli location (left or right) and probe location (left or right) were equal. And a total of 120 trials were delivered in one block (120 trials = 30 face-pairs \* 2 face locations \* 2 probe locations). The fixed cross appeared for 500ms and then a pair of facial stimuli (neutral-angry or neutral-neutral) appeared for 500ms. The probe (“\*”) then appeared and remained until a response (“F” for left and “J” for right) was made. The inter-trial interval was 1500ms.

This study used the trail-level bias score (TL-BS) as a measure of the main outcomes of this task (Zvielli et al., 2015). TL-BS is an indicator of reaction time (RT), calculated by subtracting contiguous pairs of congruent trials (probe and emotional face appeared on the same location of the screen) from incongruent trials (probe and emotional face appeared on the opposite location of the screen). Positive scores represent a tendency to be alert and attentive to emotional faces, while negative scores represent avoidance of these stimuli. A score close to zero indicated a balance of attention to emotional and neutral faces. Specifically, there are 4 TL-BS parameters: (1) Mean TL-BSpositive indicates the average value of TL-BSs > 0ms; (2) Mean TL-BSnegative indicates the average value of TL-BSs < 0ms; (3) Peak TL-BSpositive indicates the maximum TL-BS value; (4) Peak TL-BSnegative indicates the minimum TL-BS value.

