### ***Free recall and recognition task***

This study used free recall and recognition task to assess memory bias by the number of positive/negative words remembered. First, in the “encoding phase”, after a short time for a fixed cross (500ms), 30 words (15 positive words and 15 negative words) were presented randomly in turn (each word occurred for 2000ms). Participants were asked to read these words aloud and answer coding questions. The questions were divided into three categories, each corresponding to different coding conditions, including other-reference encoding (“To what extent does this word describe Jiong He?”). Jiong He is a very popular Chinese host), encoding with reference to the perception of self by others (“To what extent does this word describe what people think of you?”) and the self-reference encoding (“To what extent does this word describe you?”). Participants were asked to answer these questions using a four-point Likert scale, ranging from 1 (“Not at all”) to 4 (“Completely”). Each encoding conditions involved 10 words (5 positive words and 5 negative words), which were counterbalanced across participants. After this phase, there was a 3-minute distraction task, during which participants were guided through 40 calculation problems. They were then given 2 minutes to freely recall the words that had appeared before, regardless of the order of the words. Next, they completed a recognition task that contained 30 previously shown words and another 30 disturbing words. All of these words were presented for 4000ms in random sequence and selected from a glossary related to social anxiety, covering five aspects: communication skills, interpersonal perception, social performance, academic achievement, and social competence (Kalenzaga & Jouhaud,

2018). We assessed memory bias using accuracy rates for both positive and negative words in free recall and recognition tasks. Accuracy was calculated as: (number of correctly recalled/recognized words)  $\div$  (total number of words presented).

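### WSAP response-time indices confound the decision with the response key: one fixed mapping is described, so an arm-specific change in key or hand speed would enter both bias indices, with opposite signs

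*Combined protocol and SAP*

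**What the plan says.** The section on the word sentence association paradigm assigns F to "relevant and “J” for irrelevant". No reversal across participants or blocks is described. The same section introduces the response-time indices with the words "We also recorded the response time and calculated the bias index (BI" and defines them as "threat BI = response times (reject threat – endorse threat) and benign BI = response times (endorse benign – reject benign".

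These indices are additional measures. The percentage of threat and benign words endorsed is the result "which was prescribed as the primary result of interpretation bias".

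Counterbalancing is described for two other features. Under Interventions and study procedures, "the order of the three cognitive bias tasks was randomly counterbalanced among the participants". Under Free recall and recognition task, the words per encoding condition are those "which were counterbalanced across participants". Neither concerns the response keys.

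Under Data preparation and statistical analysis, the WSAP outcomes go into a group-by-time repeated-measures ANOVA with no term for key or hand. The electrodes are "placed in F3, FP1, FT7, C3 and FZ", with F3 as anode and the other four as returns. Only the active arm has the current sustained for the session.

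**The concern.** If every participant endorses with one key and rejects with the other, each index is a difference between decisions and also a difference between keys. The data cannot separate the two.

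Randomisation and the pre-test remove any key or hand difference that is constant over time or changes equally in both arms. They do not remove a change specific to one arm. Such a change is conceivable here: four of the five electrode sites are on the left and one (FZ) is midline, only the active arm receives sustained current, the Literature review says the current enhances or inhibits cortical activity, and the study is built to look for effects that outlast stimulation. If one hand became faster or slower in the active arm alone, a separate index could move with no change in interpretation, or a real change could be masked.

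**Working it through.** **Inputs from the documents.** Key mapping and index definitions (WSAP section); 37 per arm (Sample Size Calculation); two-sided 0.05 level and group-by-time test (Data preparation and statistical analysis).

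**Assumptions, not in the documents.** F and J are pressed with different hands. The active-arm shift h in J time minus F time is 5, 10, 20 or 40 ms. The SD of pre-to-post change in an index is 100 to 200 ms.

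**The plan's own figure.** The plan gives no number for this issue. Its sample size does reproduce: with f = 0.25, two groups, two times and an assumed correlation of 0.5, the noncentrality is 0.25² × 54 × 2 / (1 − 0.5) = 13.5, and power with 1 and 52 degrees of freedom is 0.950, that is, 27 per group. Adding 10 gives the 37 used below.

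**Step 1: substitute keys for decisions.**
- Threat BI = RT(J) − RT(F), on threat words.
- Benign BI = RT(F) − RT(J), on benign words.

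If J time minus F time rises by h in the active arm only, threat BI changes by +h and benign BI by −h. A speed change common to both keys cancels within each index.

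**Step 2: false-positive rate when interpretation does not change.** With two time points, the group-by-time test is a two-sample t test on change scores. SE = SD × √(2/37), which is 23.25 ms for SD 100 and 46.50 ms for SD 200. The noncentrality is h/SE with 72 degrees of freedom. For example, h = 20 and SD = 100 gives 20/23.25 = 0.86, and a rejection rate of 13.6%.

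| Shift h | SD 100 ms | SD 150 ms | SD 200 ms |
|---|---|---|---|
| 5 ms | 5.5% | 5.2% | 5.1% |
| 10 ms | 7.1% | 5.9% | 5.5% |
| 20 ms | 13.6% | 8.7% | 7.1% |
| 40 ms | 39.7% | 20.5% | 13.6% |

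**Step 3: does key reversal remove it?** The mapping was reversed for half of each arm in a simulation (36 per arm, 20,000 runs, shifts of 20 and 40 ms, SD 50 to 200 ms). The mean between-arm difference in BI change was about 0 ms, and rejection was 2.5% to 4.9%. With the fixed mapping the full 20 or 40 ms appeared. With 37 per arm a 19/18 split leaves h/37, about 0.5 ms for 20 ms and 1.1 ms for 40 ms.

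The rates below 5% arise because the shift now adds to the residual variance. At 40 ms and SD 50, a mapping main effect brought rejection to just under 4%, and adding group-by-mapping brought it to 5.2%. The interaction is therefore needed.

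**Step 4: the sum as a check.** Threat BI + benign BI changes by +h − h = 0, provided that h is equal on threat and benign trials. Both indices, as defined, rise with more negative interpretation, so the sum is interpretable. It has a price: with equal SDs and uncorrelated indices (assumed), a threat-only effect of d = 0.5 becomes 0.5/√2 = 0.35 on the sum, and power at 37 per arm falls from 56% to 32%.

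**The case against.** The strongest reply is that the mechanism is speculative. No statement in the documents says that stimulation changes hand speed. The stated target is the left DLPFC, C3 is one of four return sites, two-handed responding is an assumption, and no interval is given between the last stimulation and post-test. All of this stands. The point is that the design cannot separate the two explanations, not that the artefact is present.

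Second, the size depends on chosen inputs. That also stands: the documents give no reason to prefer 20 to 40 ms, and at 5 to 10 ms the effect is small or negligible.

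Third, a pure key effect would look like improvement on one index and equal worsening on the other. That does not imitate the hypothesised fall in bias across both. This limits the harm, but one index could still reach significance and be reported alone.

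A reader might infer that the dot probe task, which uses the same keys, shows how the problem is avoided, because "The number of trials for each type of stimuli location (left or right) and probe location (left or right) were equal". The documents do not support that reassurance. Trial-level scores subtract contiguous trials whose probe sides may differ, then average positive and negative values separately and take peaks. A left-right difference need not cancel.

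**Conclusion.** The confounding of decision with key follows directly from the mapping and definitions described. Its consequence is conditional: it needs a key-speed change specific to one arm, which the documents make possible but do not show. Under the stated assumptions, the false-positive rate per index runs from 5.1% (5 ms, SD 200) to 39.7% (40 ms, SD 100).

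A reader might infer that the trial's interpretation-bias result as a whole is compromised. It is not: the primary endorsement percentages do not use response times, and only the two additional indices are exposed. Nor does the text prove that no participant had reversed keys; it describes only one mapping. This is a worthwhile improvement, not a serious defect.

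**What to change.** **For further data collection.** Counterbalance the WSAP key mapping across participants within each arm, and keep each participant's mapping the same at pre-test and post-test. Include mapping and its interactions with group and time in the model for each index. The cost is a change to the task script and a few degrees of freedom.

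**For data collected under one mapping.** Keep threat BI and benign BI as the stated outcomes. Add a sensitivity analysis of their sum, and tabulate response times by key, arm and time. Do not attribute equal and opposite changes in the two indices to interpretation bias.

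The sum should not replace the separate indices. The methods text already reports assumption checks on the data, so a replacement would be a post hoc change of outcome. It would merge threat and benign interpretation, which the plan scores separately, and could lose power as shown above. It also needs usable responses in all four word-by-decision cells, so some participants may lack a value.

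If keys were in fact reversed for some participants, say so in the WSAP section and use the recorded mapping in the model.

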### ***Free recall and recognition task***

This study used free recall and recognition task to assess memory bias by the number of positive/negative words remembered. First, in the “encoding phase”, after a short time for a fixed cross (500ms), 30 words (15 positive words and 15 negative words) were presented randomly in turn (each word occurred for 2000ms). Participants were asked to read these words aloud and answer coding questions. The questions were divided into three categories, each corresponding to different coding conditions, including other-reference encoding (“To what extent does this word describe Jiong He?”). Jiong He is a very popular Chinese host), encoding with reference to the perception of self by others (“To what extent does this word describe what people think of you?”) and the self-reference encoding (“To what extent does this word describe you?”). Participants were asked to answer these questions using a four-point Likert scale, ranging from 1 (“Not at all”) to 4 (“Completely”). Each encoding conditions involved 10 words (5 positive words and 5 negative words), which were counterbalanced across participants. After this phase, there was a 3-minute distraction task, during which participants were guided through 40 calculation problems. They were then given 2 minutes to freely recall the words that had appeared before, regardless of the order of the words. Next, they completed a recognition task that contained 30 previously shown words and another 30 disturbing words. All of these words were presented for 4000ms in random sequence and selected from a glossary related to social anxiety, covering five aspects: communication skills, interpersonal perception, social performance, academic achievement, and social competence (Kalenzaga & Jouhaud,

2018). We assessed memory bias using accuracy rates for both positive and negative words in free recall and recognition tasks. Accuracy was calculated as: (number of correctly recalled/recognized words)  $\div$  (total number of words presented).

### **Data preparation and statistical analysis**

Before formal analysis, this study addressed errors and outliers in the three tasks, respectively. Trials with incorrect reactions and with RTs greater than 3000ms, lower than 200ms, or greater than  $\pm 3$  standard deviation were excluded when calculating each participants' task performances. We also treated attention, interpretation and memory bias index of  $\pm 3$  standard deviation as extreme values.

Firstly, group differences across these two groups were measured using t-tests for scale and behavioral variables, and Chi-square tests for sociodemographic variables. To explore the intervention effect of tDCS on task performance, repeated-measures ANOVA were conducted with "group" (tDCS vs. sham group) as the between-subject and "time" (pre-test vs. post-test) as the within-subject factors. The outcomes of dot probe task, word sentence association paradigm and free recall and recognition task served as dependent variables. Before the ANOVA analysis, we used the Levene test to evaluate the homogeneity of variance of the data and the results showed that the data basically satisfied the homogeneity of variance hypothesis. The Bartlett and Mauchly's test were also performed to assess the sphericity of the data, and the degrees of freedom were modified by the Greenhouse-Geisser approach if needed. For subjective scale data, we employed 2-level linear mixed-effects regression, which included three fixed effects (group, time and the interaction between group and time) and one random effect (participants). All of these analyses were conducted using SPSS 25.0 and R software. The significance level was set at  $p < 0.05$ , and the marginal significance level was set at  $p < 0.1$ . Effect sizes were reported by the partial eta-squared ( $\eta^2$ ) for ANOVA, and the Cohen's d for pairwise comparisons.

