## **Literature review**

Social anxiety is the third most common mental health issue after depression and alcohol abuse (Aune et al., 2022), particularly for youth aged from 15 to 24 (Tang et al., 2022). From the perspective of the information processing, cognitive bias is the main cause of the occurrence and maintenance of social anxiety symptoms in youth, encompassing three aspects: attention bias, interpretation bias, and memory bias (Amir & Bomyea, 2010; Kuckertz & Amir, 2014). Specifically, youth with attention bias tend to focus on the threat-related cues in the social environment (attentional vigilance), and then quickly shift their attention away (attentional avoidance). Building on attention bias, interpretation bias may lead socially anxious youth to interpret ambiguous social information negatively and attributions negative events to internal causes (Amir & Bomyea, 2010; Haller et al., 2016; Martinelli et al., 2022). In addition, memory bias refers to the tendency to recall or recognize negative stimuli, especially self-related negative information (Kuckertz & Amir, 2014; Morgan, 2010). These three cognitive biases form a self-reinforcing circle, perpetuating and exacerbating social anxiety symptoms (Nikolić, 2020).

Current treatments for cognitive bias, such as cognitive bias modification, can only yield a significant but small and unstable effect. (Enock et al., 2014; Heeren et al., 2015; Liu et al., 2017). As a result, recent research has shifted toward targeting the underlying mechanisms to achieve more robust reductions in cognitive bias, particularly at the neural circuit level (Heeren et al., 2016). High-definition transcranial direct current stimulation (HD-tDCS) is a non-invasive brain stimulation technique that delivers direct current through electrodes placed on the scalp. This current induces polarization of neuron cell membranes, thereby enhancing or inhibiting cortical activity (Kuo et al., 2013; Stein et al., 2020). For individuals with social anxiety, they often exhibit reduced regulatory control of prefrontal cortex (PFC) over the limbic system, particularly in the left dorsolateral prefrontal cortex (DLPFC) (Cremers & Roelofs, 2016). Therefore, previous tDCS studies adopted anodal tDCS to the left DLPFC and demonstrated that both attention, interpretation and memory bias in clinical populations can be significantly improved (Heeren et al., 2016; Nejati et al., 2022; Nejati et al.,

2021).

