### **Randomized and blinding**

Participants were randomly assigned to either tDCS or sham groups using a computer-generated randomization table, with a 1:1 allocation ratio. Participants remained blinded to treatment conditions throughout the intervention period. Researchers only received allocation information immediately prior to procedure implementation.

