### **Sample Size Calculation**

The required sample size was calculated using G\*Power software. Based on repeated measures analysis of variance, the sample size for each group was at least 27 (effect size = 0.25,  $\alpha$  = 0.05, power = 0.95). To avoid the impact caused by loss, an additional 10 people were included in each group, that is, 37 people. A total of 74 people

were recruited in two groups.

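### The task outcomes are analysed as change scores; adjusting for the pre-test by ANCOVA would cut the variance by about 24% at the planning correlation if pre and post SDs are equal

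*Combined protocol and SAP*

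**What the plan says.** Under the heading Data preparation and statistical analysis, the document states: "To explore the intervention effect of tDCS on task performance, repeated-measures ANOVA were conducted". Group (tDCS or sham) is the between-subject factor, and the time factor has two levels: "pre-test vs. post-test) as the within-subject factors". The outcomes of all three tasks (dot probe, word-sentence association, recall and recognition) go through this model. No covariate is named. Pre-test values enter otherwise only through between-group t-tests, which adjust nothing.

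Three other places matter:

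- Interventions and study procedures: the tasks "were assessed before the first tDCS stimulation (pre-test) and after the last tDCS stimulation (post-test"), so a pre-test value is collected by design.
- Randomized and blinding: "Participants were randomly assigned to either tDCS or sham groups", in a 1:1 ratio.
- Sample Size Calculation: "Based on repeated measures analysis of variance, the sample size for each group was at least 27", for an effect size of 0.25, with alpha and power given as "0.05, power = 0.95". Ten more per group are added for loss, giving 37 per group and 74 in total. Neither a pre-post correlation nor any SD is given.

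**The concern.** A group-by-time ANOVA with two times looks as though it makes full use of the pre-test, but it does not. It subtracts the pre-test from the post-test one for one, whatever the correlation between them. When that correlation is moderate, full subtraction adds noise that a fitted slope would avoid. In a randomised comparison the slope can be fitted without changing what is estimated.

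What is at stake is precision: the width of the interval for each task outcome, and the chance of detecting an effect smaller than the one planned for. Bias is not at issue, and neither is type I error. Smaller effects deserve some thought because the Literature review says of an existing bias treatment, cognitive bias modification, that it "can only yield a significant but small and unstable effect". That remark is not about tDCS.

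**Working it through.** **Inputs from the document.** Effect size 0.25 (read as Cohen's f, the G*Power metric for ANOVA), alpha 0.05, power 0.95, 27 per group before loss, 37 after, 1:1 allocation, two task assessments.

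**Not in the document.** The pre-post correlation r; the ratio k of post SD to pre SD; any effect other than f = 0.25. These are varied below. The 0.5 SD effect is an assumption, and effects are in pre-test SD units.

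**Step 1. Reproduce the sample size.** For the group-by-time interaction with two times, the noncentrality is λ = f² · N · 2/(1 − r), on 1 and N − 2 degrees of freedom. With N = 54 and r = 0.5, λ = 0.0625 × 54 × 2/0.5 = 13.5, and power is 0.9501. This matches the stated 27 per group. Other values of r do not: r = 0.2, 0.3, 0.7 and 0.8 give 43, 38, 17 and 12 per group. Only r from 0.500 to 0.519 gives 27.

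**Step 2. Equivalence to a change score.** f = 0.25 moves each of the four cells by 0.25 SD, so the difference in change is 4 × 0.25 = 1.0 SD. With equal SDs the change score has variance 2(1 − r), which is 1 at r = 0.5. The t-test on change has noncentrality 1/√(2/27) = 3.674, and 3.674² = 13.5, the same λ as in Step 1.

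**Step 3. Variance ratio.** Per-person variance is 1 + k² − 2rk for change and k²(1 − r²) for ANCOVA. The ratio is

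k²(1 − r²)/(1 + k² − 2rk),

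which is (1 + r)/2 when k = 1. The denominator minus the numerator is (1 − rk)², never negative, so this ratio cannot exceed 1. Estimating the slope multiplies it, on average, by 1 + 1/(N − 4): 1.014 at N = 74 and 1.020 at N = 54.

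At r = 0.5 and k = 1: 0.75 × 1.014 = 0.76 at 37 per group, and 0.75 × 1.020 = 0.765 at 27.

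**Step 4. Power and sensitivity.** Noncentral t, with 2n − 2 degrees of freedom for change and 2n − 3 for ANCOVA. At 37 per group:

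| r | k | Net variance ratio | Power at 0.5 SD, planned test | Power at 0.5 SD, ANCOVA |
|---|---|---|---|---|
| 0.2 | 1 | 0.61 | 0.39 | 0.58 |
| 0.5 | 1 | 0.76 | 0.56 | 0.68 |
| 0.7 | 1 | 0.86 | 0.78 | 0.84 |
| 0.8 | 1 | 0.91 | 0.92 | 0.94 |
| 0.5 | 1.3 | 0.925 | 0.44 | 0.47 |
| 0.7 | 1.3 | 1.005 | 0.62 | 0.62 |

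At r = 0.5 and k = 1:

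- At 27 per group, power for 0.5 SD goes from 0.44 to 0.54.
- At 37 per group, the 95% CI half-width falls from 0.46 to 0.40 SD.
- The planned ANOVA would need 49 per group to match ANCOVA with 37 (43 at r = 0.7, 41 at r = 0.8).
- At the plan's own 1.0 SD effect, power goes from 0.950 to 0.985 at 27 per group and from 0.989 to 0.998 at 37.

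If r were 0.2 instead, the 1.0 SD effect at 27 per group would have power 0.813 with the planned test and 0.954 with ANCOVA.

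**Step 5. Simulation check.** 40,000 trials per setting, 37 per group, r = 0.5, k = 1: variance ratio 0.76; power at 0.5 SD 0.567 against 0.684; type I error 0.051 against 0.049; both mean estimates 0.500.

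**The case against.** The strongest reply is that nothing here is wrong. The trial is sized for a repeated-measures ANOVA and analysed by one, both tests hold their error rate, and at the planned effect with r = 0.5 the power is already adequate. This stands, and it is why the point is only a suggestion.

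Second, the 24% depends on two quantities the document does not give. Also true: r = 0.5 is a planning value recovered from the sample size and says nothing about how any task score behaves. The gain ranges from 39% (r = 0.2, equal SDs) to none (r = 0.7, SD ratio 1.3). The downside is small: on average at most 1.4% more variance at 37 per group and 2% at 27. Single trials with a chance imbalance in the pre-test can lose more; in simulated baselines at 37 per group, the 95th percentile of this inflation was 5.5%.

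Third, three time points with r near 0.375 would also give 27 per group. The tasks are measured only twice, so this reading does not fit them, and a lower r would raise the gain.

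Fourth, the 0.5 SD effect appears nowhere in the document, and the same Literature review reports significant improvement of these biases in earlier tDCS studies. That is fair. The 0.5 SD figures show what would happen if the effect were smaller and are not a forecast.

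**Conclusion.** The point holds as an optional improvement. The planned task analysis is a change-score test that leaves the pre-test unused as a covariate. At the correlation implied by the sample size, and with equal SDs, ANCOVA would reduce the variance of the group effect by about 24%. The algebra is certain. The size of the benefit in this trial is not, because r and the SD ratio are unknown and may differ between tasks. If the true effect is 1.0 SD and r is 0.5, conclusions would rarely change. The gain matters if effects are smaller or the correlation is lower than planned.

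The calculation covers the task outcomes only. The questionnaire mixed model also has no baseline covariate, but its gain was not computed here.

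**What to change.** For each task outcome, replace the group-by-time ANOVA with ANCOVA of the post-test on group and pre-test, and report the adjusted group difference with its 95% CI. ANCOVA drops participants without a post-test, as the ANOVA does. If they are to be kept, use a mixed model that constrains the two groups to a common pre-test mean.

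The cost is a change of wording and one error degree of freedom, with no new data and no more participants. Timing needs care: the analysis section reports of the Levene test that "the results showed that the data basically satisfied the homogeneity of variance hypothesis", so data may already have been examined. If outcome data have been seen, date the change and report both the planned ANOVA and the ANCOVA.
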